7.1 ELIGIBILITY ASSESSMENT

Subjects are considered eligible for this study if they meet all of the inclusion criteria and none of the exclusion criteria as defined in **Section 6.1** and **Section 6.2**. The Investigator, co-Investigator, or sub-Investigator performing the study surgery will confirm eligibility at the time of the study surgery based upon intra-operative evaluation of the rotator cuff tear characteristics.

7.2 ENROLLMENT

Enrollment in the study occurs upon intra-operative confirmation that the subject meets all of the inclusion criteria and none of the exclusion criteria. **Patients whose rotator cuff tears do not meet study eligibility criteria at the time of the study procedure will undergo tendon repair at the discretion of the surgeon (with or without use of the Rotation Medical Rotator Cuff System) and will not be enrolled in the study**. Subjects who meet eligibility criteria will be considered enrolled into the study regardless of whether or not the device was successfully implanted. The date of the study surgery is defined as the enrollment date and all subjects who are enrolled in the study will be followed per protocol unless voluntary consent is withdrawn. All subjects enrolled into the study will be identified through a unique identifier.

7.3 **BASELINE ASSESSMENT**

The following activities must be conducted within 60 calendar days prior to enrollment:

- 1. Obtain written informed consent.
- 2. Obtain a medical history.
- 3. Perform an MRI per the Sponsor imaging guidelines.
 - Provide the Sponsor with a de-identified digital copy of, or access to, the MRI.
- 4. Assess subject eligibility based on inclusion/exclusion criteria defined in Section 6.1 and 6.2.
- 5. Administer the Constant-Murley shoulder survey.
 - *Range of motion (ROM) should be measured with a goniometer and strength should be measured with a dynamometer.*
- 6. Administer the ASES shoulder survey.
 - Completion of the ASES patient assessment section is required. Completion of the ASES physician assessment section is optional since ROM and strength are assessed during administration of the Constant-Murley survey.
- 7. Record prescription medications.
 - *Record any prescription medications the subject is taking at the time of the baseline visit to treat his/her index shoulder.*

All baseline assessments will be documented on their respective Case Report Forms (CRFs).

7.4 PROCEDURE ASSESSMENT

During the study procedure, use of any biological agents or implants aimed at augmenting tendon-to-bone healing, excluding the Rotation Medical Rotator Cuff System, are strictly prohibited. Intra-operative data along with the following study-specific procedure information will be documented on the Procedure CRF:

- 1. Device implant time
- 2. Procedure technical success
- 3. Device implant position
 - After implantation of the device, an intra-operative photograph(s) or video recording showing the implant location of the device and all tendon and bone staples will be obtained.
- 4. Intra-operative complication (if applicable; per Section 8)

Additionally, health insurance claim forms from the study surgical procedure (e.g., UB-04) will be collected by the Sponsor. Each claim form will be de-identified and serve as its own source document.

7.5 **PROCEDURE RULES**

Subjects should be scheduled to undergo the study procedure within 60 days of baseline assessment. Device implantation will be performed in accordance with the Rotation Medical Rotator Cuff System device and instrument Instructions for Use (IFUs) and may

be performed as either a mini-open or arthroscopic procedure as determined by the surgeon and subject.

Subjects with medium or large partial-thickness tears or very small full-thickness tears of the supraspinatus tendon will undergo standalone device implantation without surgical repair of the tear.

Subjects with medium or large full-thickness tears primarily of the supraspinatus tendon will undergo device implantation adjunctive to surgical repair of the tear with sutures/suture anchors.

All subjects, regardless of supraspinatus tear size, will undergo acromioplasty and bursectomy. Removal of the periosteum at the lateral edge of the supraspinatus footprint is recommended to allow visualization of the footprint and facilitate proper device positioning. Debridement of the tendon may also be performed at the discretion of the surgeon.

Concomitant surgical treatment of the biceps tendon (i.e., tenotomy, tenodesis) and coracoacromial ligament (CA) release are also permitted during the study surgery at the discretion of the surgeon. If any other concurrent rotator cuff or shoulder surgeries not specified in this protocol are performed after the subject has been enrolled, a protocol deviation will be documented on the Protocol Deviation CRF. Wound closure is performed using standard methods.

If the physician determines intra-operatively that the rotator cuff tendon tear size or quality of tissue surrounding the tear does not meet study eligibility criteria, or determines additional concomitant surgery beyond what is permitted per protocol is required to provide the best surgical outcome for the subject, the subject will not be enrolled in the study.

7.6 **POST-OPERATIVE CARE**

Post-operative care, including discharge instructions, pain management, and frequency/duration of physical therapy/rehabilitation regimen are at the discretion of the surgeon. To minimize the likelihood that the integrity or position of the device is compromised after implant, recommended rehabilitation guidelines are provided in **Table 7.2**.

Study Procedure	Rehabilitation Guidelines				
Device implant	Discard sling when comfortable				
only; without	• Progression of motion as tolerated (Passive to Active Assisted to Active)				
surgical repair	• 1 st 4 Weeks: Forward flexion limited from 0° to 100°				
	• 1 st 6 Weeks: External rotation with arm by side (No ABER)				
	• After 6 Weeks: No restrictions of motion or arm use				
Device implant	• Follow protocol for post-op surgical rotator cuff repair				
with surgical	• No additional requirements for the device				
repair	1				

Table 7-2: Post-operative	Rehabilitation Guidelines
---------------------------	---------------------------

Subjects who undergo device implantation without rotator cuff repair should follow a rehabilitation course consistent with arthroscopic subacromial decompression (ASD) alone, but with limitations on forward flexion and external rotation in abduction (ABER). Subjects who undergo device implantation with cuff repair should follow a rehabilitation course consistent with standard rotator cuff repair.

7.7 FOLLOW-UP ASSESSMENTS

All subjects will undergo post-operative study assessments at 3 months, 1 year, and 2 years after discharge from the study procedure as described below and summarized in **Table 7.1**.

7.7.1 3-Month (± 15 Days) Follow-Up

- 1. Perform an MRI per the Sponsor imaging guidelines.
 - Provide the Sponsor with a de-identified digital copy of, or access to, the MRI.
- 2. Administer the Constant-Murley shoulder survey.
 - Range of motion (ROM) should be measured with a goniometer and strength should be measured with a dynamometer. NOTE: Strength or ROM testing at 3-Month Follow-Up may not be possible due to subject discomfort or ongoing rehabilitation and therefore missed or incomplete strength or ROM testing at this visit will not be considered as a protocol deviation.
- 3. Administer the ASES shoulder survey.
 - Completion of the ASES patient assessment section is required. Completion of the ASES physician assessment section is optional since ROM and strength are assessed during administration of the Constant-Murley survey.
- 4. Administer the recovery/satisfaction questionnaire.
- 5. Record prescription medications.
 - *Record any prescription medications the subject is taking at the time of the follow-up visit to treat his/her index shoulder.*
- 6. Record any new adverse events and update the status of any ongoing, previouslyreported adverse events.
- 7. Report any new revision/additional shoulder surgeries performed on the index shoulder.

7.7.2 1-Year (± 45 Days) Follow-Up

- 1. Perform an MRI per the Sponsor imaging guidelines.
- Provide the Sponsor with a de-identified digital copy of, or access to, the MRI.
- 2. Administer the Constant-Murley shoulder survey.
 - *Range of motion (ROM) should be measured with a goniometer and strength should be measured with a dynamometer.*
- 3. Administer the ASES shoulder survey.
 - Completion of the ASES patient assessment section is required. Completion of the ASES physician assessment section is optional since ROM and strength are assessed during administration of the Constant-Murley survey.
- 4. Administer the recovery/satisfaction questionnaire.
- 5. Record prescription medications.

- *Record any prescription medications the subject is taking at the time of the follow-up visit to treat his/her index shoulder.*
- 6. Record any new adverse events and update the status of any ongoing, previouslyreported adverse events.
- 7. Report any new revision/additional shoulder surgeries performed on the index shoulder.

7.7.3 2-Year (± 90 Days) Follow-Up

- 1. Perform an MRI per the Sponsor imaging guidelines.
 - Provide the Sponsor with a de-identified digital copy of, or access to, the MRI.
- 2. Administer the Constant-Murley shoulder survey.
 - *Range of motion (ROM) should be measured with a goniometer and strength should be measured with a dynamometer.*
- 3. Administer the ASES shoulder survey.
 - Completion of the ASES patient assessment section is required. Completion of the ASES physician assessment section is optional since ROM and strength are assessed during administration of the Constant-Murley survey.
- 4. Administer the recovery/satisfaction questionnaire.
- 5. Record prescription medications.
 - *Record any prescription medications the subject is taking at the time of the follow-up visit to treat his/her index shoulder.*
- 6. Record any new adverse events and update the status of any ongoing, previouslyreported adverse events.
- 7. Report any new revision/additional shoulder surgeries performed on the index shoulder.

The results of all follow-up assessments will be documented on their respective CRFs. Each reportable adverse event (Section 4.1.1) will be documented on an Adverse Event CRF.

7.8 UNSCHEDULED FOLLOW-UP

Any unscheduled return visits to the study center/Principal Investigator for non-standard of care evaluation for ongoing shoulder-related issues will be documented on a CRF. The reason for the visit and visit outcome will be documented. If an MRI, ASES survey, or Constant-Murley survey is completed, these assessments should also be documented on the appropriate CRFs. Visits required by the protocol or visits for routine post-operative follow-up are not considered unscheduled and do not need to be reported as an unscheduled visit.

7.9 REVISION/ADDITIONAL SHOULDER SURGERY

If the subject has additional or revision shoulder surgery on the index shoulder at any time during the follow-up period, the clinical site should make every effort to collect the procedure/operative notes for the procedure and complete the Revision/Additional Shoulder Surgery CRF. One (1) Revision/Additional Shoulder Surgery CRF should be completed for all surgeries performed on a single date. If a subject has multiple surgeries on the index shoulder on different dates, the Revision/Additional Shoulder Surgery CRF should be completed for each surgery date.

7.10 EARLY WITHDRAWAL OR LOST TO FOLLOW-UP

If a subject wishes to withdraw from the study at any time, (s)he is able to do so voluntarily without having to justify it and without affecting her/his relationship with the Investigator.

Also, an Investigator may withdraw a subject from the study at any time if (s)he thinks it is in the subject's best interest.

The subject's future management will not be changed by a decision, voluntary or otherwise, to withdraw from the study.

All reasonable efforts should be made to retain the subject in this clinical study until completion of the clinical assessments at each follow-up visit. A subject will be considered "lost to follow-up" after a minimum of 2 documented phone calls to the subject were completed by a member of the study staff and a certified letter was sent to the last known address by a traceable method (e.g., certified mail; courier; commercial shipping/transport company).

Should subject early withdrawal or termination of participation occur, the termination information and the date of last contact with the subject should be recorded in the subject's records and included on the End of Study CRF.

7.11 END OF STUDY

Subjects will be exited upon successful completion of follow-up assessments or at the time of withdrawal or lost-to-follow-up. An End of Study CRF will be completed at the time of study completion or discontinuation.

8 ADVERSE EVENT DEFINITIONS AND REPORTING

Adverse events are to be reported from the time of enrollment through the last study follow-up visit.

8.1 DEFINITION OF ADVERSE EVENT (AE)

An Adverse Event (AE) is any undesirable clinical occurrence experienced by the subject. Any underlying disease that was present at the time of enrollment and prior to surgery (i.e. rotator cuff tendon tear) that persists after surgery is not considered an AE.

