4.4 SECONDARY OUTCOME MEASURES

4.4.1 Safety

Safety will be evaluated by any of the following adverse events that occur over the duration of the study:

- 1. Any death
- 2. All serious adverse events (SAE) regardless of relation to the device or procedure
- 3. Any non-serious adverse event (AE) that is classified as either device or procedurerelated
- 4. Any unanticipated adverse device effect (UADE)

Adverse events will be summarized by relation to the study devices or study procedure. Overall occurrence rate by event type will also be calculated.

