8.2 SERIOUS ADVERSE EVENT (SAE)

A Serious Adverse Event (SAE) includes any of the following events:

- Results in death
- Is life threatening
- Requires subject hospitalization or prolongation of existing hospitalization
- Requires invasive surgical intervention to fix the problem
- Results in persistent or significant disability/incapacity
- Is considered an important medical event

An important medical event that may not meet one of the above definitions might be considered as an SAE if it jeopardizes the health of the subject or requires surgical intervention to prevent one of the outcomes listed in the above definition. Elective hospitalization after the procedure that was planned prior to subject enrollment is not to be considered as an SAE.

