8.3 UNANTICIPATED ADVERSE DEVICE EFFECT (UADE)

An Unanticipated Adverse Device Effects (UADE) is any serious adverse effect on health or safety, or any life-threatening problem or death caused by, or associated with, a device, if that effect was not previously identified in nature, severity, or degree of incidence in protocol, subject informed consent form, or application, or any other unanticipated serious problem associated with a device that relates to the rights, safety, or welfare of subjects. Anticipated adverse events are listed as known risks in **Section 12.1**.

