12 RISKS AND BENEFITS

12.1 RISKS AND RISK MITIGATION

Study patients will be informed of all known potential side effects and complications associated with the study assessments and study procedure prior to enrollment in the study.

There are no known incremental risks to the subject for participating in the study. The risks associated with participating in this study are the same as if the patient is treated outside of the study using the same commercially-available device and include the following potential risks of rotator cuff surgery performed under general or regional anesthesia:

- Tissue inflammation
- The need for repeated surgery because tendons do not heal properly or tear again
- Pain or stiffness that won't go away
- Fever and/or infection
- Complication from anesthesia
- Nerve or blood vessel damage
- Adverse reaction to device

In addition, subjects will be required to undergo MR imaging. MRI is generally a welltolerated procedure and there is no ionizing radiation involved with MR imaging The potential risks are minimal and include claustrophobia, coil element heating and peripheral nerve stimulation, although the latter two are considered highly unlikely, given that the subjects will be imaged within preset safety guidelines to eliminate peripheral nerve stimulation. Coil element heating ranges from a mild sensation of heat to a potential burn. This is considered highly unlikely, as the coils have all undergone extensive testing and clinical use, and special pads are placed surrounding all contact points.

All Investigators will undergo training and subjects will be screened and evaluated for medical histories/conditions that may compromise safe, successful completion of any of the study assessments or performance of the device. Subjects with a known hypersensitivity to bovine-derived materials will not be enrolled in the study.

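### Section 8.1 excludes a persisting cuff tear from the AE definition while 8.2, 8.3 and 12.1 point the other way, so re-operations for unhealed tears can be left out of the SAE rate

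*Combined protocol and SAP*

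**What the plan says.** Five parts of the protocol bear on how a re-operation for an unhealed tear is counted.

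- **Section 8.1** opens broadly: "An Adverse Event (AE) is any undesirable clinical occurrence experienced by the subject". It then excludes an underlying disease that was present at enrollment and before surgery, and names the tear: "i.e. rotator cuff tendon tear) that persists after surgery is not considered an AE". Nothing is said about a persisting tear that needs another operation.
- **Section 8.2** lists what makes an event serious, including "Requires invasive surgical intervention to fix the problem". Its one stated exclusion is "Elective hospitalization after the procedure that was planned prior to subject enrollment is not to be considered as an SAE".
- **Sections 8.3 and 12.1** are linked. Section 8.3 says "Anticipated adverse events are listed as known risks in" Section 12.1, and that list contains "The need for repeated surgery because tendons do not heal properly or tear again".
- **Section 4.4.1** builds the safety outcome from adverse events only: deaths, SAEs, device- or procedure-related non-serious AEs, and UADEs. The SAE item reads "All serious adverse events (SAE) regardless of relation to the device or procedure". Re-operation is not an item of its own.
- **Section 7.9 and Table 7-1 (footnote 6)** require further surgery on the index shoulder to be reported. The site is to "complete the Revision/Additional Shoulder Surgery CRF", one form per surgery date. No primary or secondary outcome in Section 4 draws on that form.

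**The concern.** Under Section 7.5, subjects meeting criterion 2A receive the implant without surgical repair of the tear. If such a tear does not heal and the subject returns to the operating room, that operation is something a reader of the safety results would expect to see counted. Section 8.1 gives a site grounds to conclude that no AE occurred, because the condition treated is the tear the subject came in with. Sections 8.2, 8.3 and 12.1 give another site grounds to report an SAE for the same history.

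Two things are at stake. The SAE rate could omit some re-operations for non-healing. And with up to 15 sites (Section 4.1), differences in reported rates between sites could reflect how 8.1 was read rather than what happened to subjects. The study has a single arm, so no comparator coded under the same convention would show the gap.

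**Working it through.** The point rests on the text; the arithmetic only shows scale.

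**Step 1. Follow one case under both readings.** Take a 2A subject whose original tear never closed and who has a second operation on the index shoulder because of it.

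| Question | Literal use of 8.1 | Use of 8.2, 8.3 and 12.1 |
|---|---|---|
| Is it an AE? | No: the original tear has persisted | Yes: the need for repeat surgery is a new undesirable occurrence and a listed anticipated event |
| Is it an SAE? | Not reached | Yes: it meets the surgical-intervention criterion |
| Forms filed | Revision/Additional Shoulder Surgery form only | That form and an Adverse Event form |
| Counted under 4.4.1? | No | Yes, as an SAE, whatever its relation to the device |

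Once the case is accepted as an AE, the surgery criterion makes it serious and 4.4.1 counts it regardless of relatedness. The count therefore turns entirely on how 8.1 is read.

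**Step 2. Look for another route into the results.**

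- UADE (8.3): repeat surgery for non-healing is named in 12.1, so by its nature it is anticipated and would not ordinarily enter here.
- Re-tear (4.3.4): this is defined by a new defect. A tear that never closed need not qualify.
- Fill-in and defect progression (4.3.3): non-healing in standalone subjects is assessed here, but as an MRI finding. It does not count operations.
- Revision form (7.9): the operation is recorded, but no outcome uses the form, and no section asks for it to be matched to AE records.

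The operation is therefore on file, yet it can be absent from every defined outcome summary.

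**Step 3. Look for a rule of precedence.** None appears in 8.1 to 8.4, 4.4.1 or 7.9.

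**Step 4. Scale.** The documents give no rate of re-operation for a persisting tear and do not fix the 2A share. Assume a rate *r* of 2% to 10%. Expected events = N × *r*.

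- All subjects at risk, N = 150 (the Section 4.1 maximum): 150 × 0.02 = 3; 150 × 0.10 = 15.
- Only 2A at risk and 2A is half (assumption), N = 75: 75 × 0.02 = 1.5; 75 × 0.10 = 7.5.

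The chance of at least one such event is 1 − (1 − *r*)^N. At 2% this is 1 − 0.98^150 = 0.95 for N = 150, and 1 − 0.98^75 = 0.78 for N = 75. These are events whose SAE status would depend on the reading of 8.1, not events certain to be lost.

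**The case against.** The best reply is that the sections, read together, favour reporting. Section 8.1 excludes a disease that persists, not a fresh occurrence that arises from it. A second operation fits the broad opening definition, meets the 8.2 criterion, is not caught by the only exclusion in 8.2, and appears in the list that 8.3 calls anticipated adverse events. Moreover, the surgery is recorded, operative notes are sought, and failure to fill in is part of a primary MRI outcome. Safety is a secondary, descriptive outcome with no hypothesis attached, so no primary inference changes.

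Much of this stands. It means 8.1 permits the omission without requiring it, and that neither the operation nor the non-healing is hidden from the study database. It does not remove the conflict: the protocol leaves the choice to each site, and the literal choice drops the event from the safety outcome.

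Some stronger readings are tempting but unsupported:

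- A reader might infer that such a re-operation can never be an SAE. That follows only from the strictest reading of 8.1, and the sections above support the opposite.
- A reader might infer that worsening tears, new re-tears, or stiffness after surgery also drop out. The exclusion reaches only what persists. Worsening and a new defect are not persistence, and stiffness arising after surgery is not the pre-existing tear.
- A reader might size the problem from the earlier clinical study or the literature in Section 1. The one re-operation described there was a debridement of the bursa, with tendon healing reported as not compromised. The cited re-tear range concerns tears that had been completed and repaired, and it is a structural rate, not a re-operation rate. Neither measures re-operation for a persisting, unrepaired tear.

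**Conclusion.** The concern holds as an unresolved conflict between Section 8.1 and Sections 8.2, 8.3 and 12.1. Re-operations for tears that did not heal, chiefly in the standalone 2A group, can be left out of the SAE rate and coded inconsistently across sites. On assumed rates of 2% to 10%, the events in doubt number about 3 to 15 if all 150 subjects are at risk, or 1.5 to 7.5 if only 2A subjects are and they make up half. Both the rates and the share are assumptions; the conflict itself depends on neither. The primary thickness hypothesis is unaffected. The wording should still be corrected, because the safety summary is where a reader would look for these operations.

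**What to change.** In Section 8.1, state that persistence of the index tear alone is not an AE, but that a persisting tear leading to surgery on the index shoulder is an AE, assessed for seriousness under 8.2. This brings 8.1 into line with 8.2, 8.3 and 12.1.

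In Section 4.4.1, require each Revision/Additional Shoulder Surgery form to be reconciled with an AE record, and report all index-shoulder re-operations in the safety summary, separately for 2A and 2B.

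The cost is a few sentences and a reconciliation check on forms already collected, with no added burden on subjects and no change to treatment. The downside is that the reported SAE rate may be slightly higher.
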